#### **Early Asthmatic Response (EAR) and Late Asthmatic Response (LAR)**

During a session in the EEU, an EAR is expected to be mild or moderate. As soon as the patient has a drop in FEV1 of 20% and/or asthma symptoms, the patient will be removed from the EEU and will be treated with short-acting  $\beta$ 2 agonist every 20 minutes for 1 hour if necessary. Patients will stay under supervision in the observation room during 6 hours after leaving the EEU and FEV1 will be monitored every 30 minutes. During this 6-hour monitoring period, a LAR can appear with a drop in FEV1 of 15% and will be treated with short-acting  $\beta$ 2 agonist and corticosteroids if necessary. Approximately at the end of the 6-hour monitoring period, patients will undergo a physical exam and vital signs, including spirometry, and will be discharged home if there are no abnormal findings and if FEV1  $\geq 90\%$  of baseline. If FEV1 is  $< 90\%$  of the baseline value, patients will continue to be monitored at the clinic until the patient meets criteria for discharge. FEV1 will be monitored at home for approximately 18 hours after leaving the clinical unit (a total of 24 hours of monitoring from the end of the EEU exposure). If there is a 30% drop in FEV1 during home monitoring, the investigator(s) will receive an alarm by email to inform about the change in spirometry and the patient will be contacted and evaluated by a medical doctor.

Severe bronchoconstriction will be treated with oxygen, short-acting  $\beta$ 2 agonist by nebulization, and oral systemic corticosteroids.

Under the extremely rare circumstance that patients experience a severe systemic reaction to the EEU (anaphylaxis), with arterial hypotension, angioedema, or urticaria, patients will be treated with adrenaline 0.3 mg IM and will be transferred to the hospital emergency room, which is located within a 5-minute walk of the clinical trial unit.

## 7.5. **Blinding**

Study patients, the principal investigators, and study site personnel (with the exception of the study pharmacist) will be blinded to all randomization assignments throughout the study. The Regeneron Study Director, Medical Monitor, Study Monitor, and all other Regeneron personnel who will be in regular contact with the study site will be blinded to all patient randomization assignments. Study drug kits coded with a medication numbering system will be used. In order to maintain the blind, lists linking these codes with product lot numbers will not be accessible to blinded individuals involved in study conduct. Although the designated study pharmacist(s)/designee at the study site are unblinded, the treatment assignment will not be provided to site personnel, including the investigator, at any time during the conduct of the study, except in the case of a true emergency.

Selected individuals who are not responsible for the treatment or clinical evaluation of patients may have access to unblinded data as needed for safety review or other data review.

### 7.5.1. **Emergency Unblinding**

Unblinding of treatment assignment for a patient may be necessary due to a medical emergency or any other significant medical event (eg, pregnancy).

If unblinding is required:

- Only the investigator will make the decision to unblind the treatment assignment
- Only the affected patients will be unblinded
- The designated study pharmacist(s)/designee at the study site will provide the treatment assignment to the investigator. If there is no study pharmacist, the investigator for the site will unblind the patient
- The investigator will notify Regeneron and/or designee as soon as possible after unblinding the patient

Treatment assignment is not to be provided to site personnel, other than the unblinded study pharmacist (when applicable), at any time during the conduct of the study, except in the case of a true emergency. In the event that there is no study pharmacist, the individual at the site fulfilling that role will be the only unblinded member of the site personnel.

## 7.6. **Method of Treatment Assignment**

Approximately 60 patients will be randomized in a 1:1 ratio to receive either 600 mg REGN1908-1909 or placebo according to a central randomization scheme provided by an interactive voice response system (IVRS)/interactive web response system (IWRS) to the designated study pharmacist (or qualified designee).

## **7.7. Treatment Logistics and Accountability**

### **7.7.1. Packaging, Labeling, and Storage**

A medication numbering system will be used in labeling investigational study drug. Lists linking medication numbers with product lot numbers will be maintained by the groups (or companies) responsible for study drug packaging.

Study drug will be stored at the site at a temperature of 2°C to 8°C; storage instructions will be provided in the pharmacy manual.

### **7.7.2. Supply and Disposition of Treatments**

Study drug will be shipped at a temperature of 2°C to 8°C to the investigator or designee at regular intervals or as needed during the study. At specified time points during the study (eg, interim site monitoring visits), at the site close-out visit, and following drug reconciliation and documentation by the site monitor, all opened and unopened study drug will be destroyed.

### **7.7.3. Treatment Accountability**

All drug accountability records must be kept current.

The investigator must be able to account for all opened and unopened study drug. These records should contain the dates, quantity, and study medication:

- dispensed to each patient,
- returned from each patient (if applicable), and
- disposed of at the site or returned to the sponsor or designee

All accountability records must be made available for inspection by the sponsor and regulatory agency inspectors; photocopies must be provided to the sponsor at the conclusion of the study.

### **7.7.4. Treatment Compliance**

All drug compliance records must be kept current and made available for inspection by the sponsor and regulatory agency inspectors.

## **7.8. Concomitant Medications**

Any treatment administered from the time of informed consent to the end of the treatment final study visit will be considered concomitant medication. This includes medications that were started before the study and are ongoing during the study. This excludes all rescue treatment kit medications, taken at home within 24 hours from the EEU exposure. Rescue medications taken from the kit within 24 hours of EEU exposure will be collected separately.

**7.8.1. Prohibited Medications**

1. Use of these concomitant medications within the following time period is preceding any screening visit or any EEU visit:

(NOTE: Patients may be rescheduled 1 time for the screening visit or EEU visit after the time period for taking these concomitant medications has passed.)

- a. Topical or systemic first generation H1 antihistamines (5 days)
- b. Topical or systemic second generation H1 blockers (7 days)
- c. Systemic anti-H2 (8 days)
- d. Atemizole (6 weeks)
- e. Cromoglycates, leukotriene modifiers (7 days)
- f. Systemic steroid treatment (8 weeks prior to screening and during the study)

(NOTE: systemic steroid treatment is allowed if clinically indicated for a LAR treatment after exposure to cat allergen in the EEU.)

- g. Topical steroids (48 hours)
- h. Short-acting  $\beta$ 2 agonists (8 hours)
- i. Long-acting  $\beta$ 2 agonists (eg, salmeterol) (36 hours)
- j. Ultra-long-acting  $\beta$ 2 agonists (eg, indacaterol, vilanterol, olodaterol) (48 hours)
- k. Anticholinergics eg, Ipratropium (Atrovent 40  $\mu$ g) (12 hours)
- l. Long-acting anti-muscarinic agents (7 days)
- m. Methylxanthines (eg, oral theophylline) (24 hours)
- n. Intramuscular corticosteroids (3 months prior to screening and during the study)
- o. Systemic or topical calcineurin inhibitors (14 days prior to screening and during the study)
- p. Tricyclic antidepressants/antipsychotics (14 days)
- q. Topical decongestants (72 hours)
- r. Caffeine-containing drinks or products (8 hours of EEU visits only)

2. History of SIT with cat allergen or vaccines against cat allergy within 5 years of screening
3. SIT with any allergen within 6 months of screening
4. Beta-blockers during the study period
5. Immunomodulatory therapy, anti-IgE, or other biological, agent-based antagonist therapy is not allowed in the 6 months prior to baseline (eg, cyclosporine) or during the study
6. Change in prescription medications within 4 weeks before screening
7. Aspirin and any nonsteroidal anti-inflammatory drug

NOTE: paracetamol is allowed to be used for occasional pain relief.

8. Active treatment for respiratory infections (antiviral, antifungals, or antibiotics) within 4 weeks prior to screening or EEU

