### **7.8.2. Permitted Medications**

Use of standard-of-care medications not listed as prohibited will be allowed. Treatment for acute reactions is allowed during the study (See Section [7.4](#)).

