8. Titrated SPT with Serial Allergen Titration with cat allergen will be performed at screening visit 3, days 29, 85, and 113. On days when an allergen challenge is performed, the test will be performed prior to allergen challenge.
9. FeNO is assessed during screening, Visit 4 and then 24 hours after EEU exposure at day 30 and day 86.
10. All safety assessments performed at screening have to be normal and checked against the inclusion/exclusion criteria prior to REGN1908-1909 administration on day 1 (baseline).
11. On day 1, vital signs are taken prior to PK draw, prior to REGN1908-1909 administration, and at 2 hours ( $\pm 10$  min) after completion of the injection.

12. Vital signs are taken prior to entry into the EEU, at exit from the EEU, and prior to leaving the clinical trial unit, and any additional times as needed.
13. Telephone call to collect AEs and concomitant medications, including any medications used from the rescue treatment kit, up to 24 hours after the EEU exposure.
14. Total blood draw at any visit will never exceed 60 mL. Blood volumes are never to exceed 350 mL in 12 weeks.
15. Samples are collected prior to administration of REGN1908-1909.
16. On day 1, urine pregnancy test is completed prior to administration of REGN1908-1909 in women of childbearing potential. Postmenopausal women do not need urine pregnancy testing.
17. Total IgE and allergen-specific serum IgE levels (Fel d 2, Fel d 4, Fel d 7).
18. Genomic analysis is mandatory for all patients enrolling in the study. One DNA sample is to be collected on day 1/randomization, but if this sample collection was omitted at baseline, it can be collected at any subsequent visit. [REDACTED]
19. PK samples are drawn at any time in the outpatient visit day from day 8 through day 113 (end of study) visit.
20. After exiting the EEU, patients are monitored outside the EEU in an observation room for approximately 6 hours.
21. Patients will be observed for 6 hours in the observation room after receiving a single dose of REGN1908-1909 or placebo.
22. Blood draws should be performed before the EEU exposure
23. Cat EEU visit 3 and visit 6 must be spaced at least 3 weeks apart
24. Assessments and procedures at the unscheduled visit(s) are to be performed at the discretion of the principle investigator.
25. Screening visits 1 and 2 may be combined into 1 visit if the patient has a historical, positive cat SPT or cat IgE that was completed in the last 12 months.

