4.4. Rescue Medication/or Prohibited Medication During Study

The use of the following concomitant medications is not permitted during the study:

1. Use of these concomitant medications within the following time period preceding any screening visit or any EEU visit:

(NOTE: Patients may be rescheduled 1 time for the screening visit or EEU visit after the time period for taking these concomitant medications has passed.)

- a. Topical or systemic first generation H1 antihistamines (5 days)
- b. Topical or systemic second generation H1 blockers (7 days)
- c. Systemic anti-H2 (8 days)
- d. Atemizole (6 weeks)
- e. Cromoglycates, leukotriene modifiers (7 days)
- f. Systemic steroid treatment (8 weeks prior to screening and during the study)

(NOTE: systemic steroid treatment is allowed if clinically indicated for a LAR treatment after exposure to cat allergen in the EEU.)

- g. Topical steroids (48 hours)
- h. Short-acting β 2 agonists (8 hours)
- i. Long-acting β 2 agonists (eg, salmeterol) (36 hours)
- j. Ultra-long-acting β 2 agonists (eg, indacaterol, vilanterol, olodaterol) (48 hours)
- k. Anticholinergics eg, Ipratropium (Atrovent 40 μ g) (12 hours)
- l. Long-acting anti-muscarinic agents (7 days)
- m. Methylxanthynes (eg, oral theophylline) (24 hours)
- n. Intramuscular corticosteroids (3 months prior to screening and during the study)
- o. Systemic or topical calcineurin inhibitors (14 days prior to screening and during the study)
- p. Tricyclic antidepressants/antipsychotics (14 days)
- q. Topical decongestants (72 hours)

- r. Caffeine-containing drinks or products (8 hours of EEU visits only)
2. History of systemic immunotherapy (SIT) with cat allergen or vaccines against cat allergy within 5 years of screening
3. SIT with any allergen within 6 months of screening
4. Beta-blockers during the study period
5. Immunomodulatory therapy, anti-IgE, or other biological, agent-based antagonist therapy (eg, cyclosporine) is not allowed in the 6 months prior to baseline or during the study
6. Change in prescription medications within 4 weeks before screening
7. Aspirin and any nonsteroidal anti-inflammatory drug

NOTE: paracetamol is allowed to be used for occasional pain relief.

8. Active treatment for respiratory infections (antiviral, antifungals, or antibiotics) within 4 weeks prior to screening or EEU

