4.5.3. Exploratory Efficacy Variables

The exploratory efficacy variables are:

- Time to Late Asthmatic Response (LAR) on days 8, 29, 57, and 85
- Time to Any Asthmatic Response on days 8, 29, 57, and 85
- Change and percent change from FeNO (parts per billion) (adjusted for the pre-challenge baseline) from baseline to days 30 and 86
- Change and percent change in the skin prick test with serial allergen titration, measured by AUC of the wheal sizes (diameter) over log-transformed allergen concentrations with cat allergen from baseline to day 29, 85, and 113

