hour observation period, or in the at-home monitoring period, will be treated as the event time. If the subject experiences no asthmatic reaction at a given Allergen Challenge visit, the patient's time will be censored at 24 hours. Kaplan-Meier estimates and curves will be produced for each visit.

The presence or absence of any asthma exacerbation (EAR or LAR) in the REGN1908-1909 treatment group as compared to placebo will be tested using a Fisher's Exact Test.

Individual spaghetti plots and mean plots of the percent change in FEV1 over time will also be examined. LOCF will be used in the calculation for any graphical displays of the mean change in FEV1 over the Cat Allergen Challenge.

The peak TNSS and TOSS and change from pre-challenge baseline to peak TNSS and TOSS across EEU challenge visits may also be examined using MMRM models.

The change and percent change from the Baseline Cat Allergen Challenge in the Fractional exhaled Nitric Oxide (FeNO) (adjusted for the pre-challenge baseline) will be explored using an MMRM model, with the treatment, visit, and treatment by visit interaction, and use of steroid rescue medications within 24 hours of the EEU challenge as factors. The time in EEU will be included as a covariate in the model.

The skin prick test with serial allergen titration with cat allergen will also be compared between treatment groups using an MMRM model, with the treatment, visit and treatment by visit interaction as factors.

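### The H1-antihistamine washouts do not reach the day 113 titrated skin prick test, and the SAP analyses that reading with no allowance for recent antihistamine use

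*Protocol*

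**What the plan says.** Protocol 7.8.1 item 1 lists drugs that may not be used "within the following time period is preceding any screening visit or any EEU visit". Items 1a and 1b set 5 days for first-generation and 7 days for second-generation H1 antihistamines. SAP 4.4 item 1 keeps the same limit: "within the following time period preceding any screening visit or any EEU visit". Protocol 7.8.2 adds: "Use of standard-of-care medications not listed as prohibited will be allowed".

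The titrated skin test, under footnote 8 of Protocol 8.1.1, "will be performed at screening visit 3, days 29, 85, and 113". Protocol 5.1 places challenges after randomization on days 8, 29, 57 and 85, and describes the week 16 visit as a safety follow-up four weeks after the last challenge. Protocol 8.1.2 gives patients who withdraw the same closing assessments at an early termination visit.

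SAP 4.5.3 makes change and percent change in wheal AUC an exploratory variable, "with cat allergen from baseline to day 29, 85, and 113". SAP 5.6.3 states the analysis: "The skin prick test with serial allergen titration with cat allergen will also be compared between treatment groups using an MMRM model". The factors are treatment, visit and their interaction.

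**The concern.** Protocol 3.2.4 describes the skin reaction as an early-phase response marked by histamine release, so an H1 antihistamine acts on the read-out itself. The patients have allergic rhinitis, the protocol's introduction names antihistamines as a treatment for rhinoconjunctivitis, and every patient leaves each challenge with a rescue kit that contains them (Protocol 7.2). On the wording of 7.8.1, a patient who takes an antihistamine in the week before day 113 breaks no stated rule and is tested under it.

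The day 113 value is then compared with a baseline obtained under washout. It is the only titrated reading scheduled after day 85, so it informs how long the pharmacodynamic effect lasts. Nothing in the planned model separates study-drug effect from antihistamine effect at that visit. The same SAP section does include steroid rescue use as a factor for FeNO, so the authors allowed for medication there but not here.

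**Working it through.** The documents give no figure for this point, so there is none to reproduce. The check has two parts.

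**1. Is day 113 outside the washouts?**

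| Titrated test | Screening or EEU visit? | Antihistamine washout applies? |
|---|---|---|
| Visit 3 (baseline) | Yes, both | Yes |
| Day 29 | Yes, EEU | Yes |
| Day 85 | Yes, EEU | Yes |
| Day 113 | Neither | No |
| Early termination | Neither | No |

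Day 85 to day 113 is 113 − 85 = 28 days. With the ±3-day windows in Table 1 the range is (113 − 3) − (85 + 3) = 22 to (113 + 3) − (85 − 3) = 34 days. The 5 or 7 days before the day 113 test therefore lie wholly after the last visit that a washout protects.

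**2. What could it do to the comparison?**

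Scale wheal AUC so that a placebo patient without antihistamine has the value 1. Let r be the true relative reduction on drug, qP and qA the proportions of recent antihistamine users on placebo and on drug, and s the proportional suppression in users. None of these is in the documents. I assume r = 0.30 and s = 0.40 to 0.80, with the same proportional suppression in both arms and use unrelated to underlying wheal size.

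- Placebo mean = 1 − qP·s
- Drug mean = (1 − r)(1 − qA·s)
- Contrast = placebo mean − drug mean; it equals r when nobody uses an antihistamine
- Shift in contrast = −qP·s + (1 − r)·qA·s

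| Use, placebo / drug | Shift | s = 0.40 | s = 0.80 | Contrast seen (true 30 points) |
|---|---|---|---|---|
| 20% / 20% | −0.20s + 0.14s = −0.06s | −2.4 | −4.8 | 27.6 to 25.2 |
| 20% / 10% | −0.20s + 0.07s = −0.13s | −5.2 | −10.4 | 24.8 to 19.6 |
| 10% / 20% | −0.10s + 0.14s = +0.04s | +1.6 | +3.2 | 31.6 to 33.2 |

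Shifts are in percentage points of the unmedicated placebo AUC. Equal use dilutes the contrast. More use on placebo biases it towards no effect. More use on drug can inflate it.

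**The case against.** **The endpoint is minor.** This stands. The test is exploratory, and the protocol objective for it (2.3.1) names only days 29 and 85, both under washout. It does not appear in the SAP 10.1 summary of analyses. A reader might infer that the efficacy conclusions are at risk, but the primary and secondary endpoints come from washed-out EEU days.

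**A washout may exist elsewhere.** Protocol 8.2 refers its procedures to a Study Operations Manual that is not available here. It may set a pre-test rule. Neither the protocol nor the SAP mentions one for day 113, so the gap is in these two documents and not established in practice.

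**SAP 4.4 opens by saying the listed drugs are not permitted during the study.** Item 1 then restores the screening and EEU limit, so the opening does not close the gap. The per-protocol set does not help either: it removes users of prohibited medication, which this use is not, and SAP 10.1 lists that set only for time to EAR.

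**Use can be inspected anyway.** SAP 5.3 summarises concomitant medication, so use will be visible, but the summaries do not tie it to the interval before the test.

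Three stronger readings are tempting and do not hold:

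- *That with equal use a waning drug would appear to hold.* The planned comparison is between groups. At equal 20% use the placebo mean falls by 0.20s (8 to 16 points) and the drug mean by 0.14s (5.6 to 11.2), so the drug looks weaker. Only a within-arm reading could suggest persistence.
- *That bias is simply the difference in use times the suppression.* That holds only if the drug has no effect. It gives zero for equal use, and 4 to 8 points for 20% against 10%, where the full expression gives 5.2 to 10.4.
- *That every item 1 washout leaves the same gap.* Systemic and intramuscular corticosteroids and calcineurin inhibitors are also barred during the study, apart from steroids for a late asthmatic response. For bronchodilators the documents give no route to the wheal.

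**Conclusion.** The point holds as a minor one. As written, the timed H1-antihistamine washouts cover the titrated test at visit 3, day 29 and day 85 but not at day 113 or early termination, and the SAP makes no allowance for the difference. The day 113 contrast may be diluted or biased. The illustrated losses, 2.4 to 4.8 points for equal 20% use and 5.2 to 10.4 for 20% against 10%, rest entirely on assumed use, suppression and true effect. The documents support neither a particular size nor a direction for unequal use. The conclusion also assumes that the unseen manual sets no washout for this test.

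**What to change.** In SAP 5.6.3, flag any day 113 or early-termination titrated skin test where an H1 antihistamine was taken within the interval already listed in 7.8.1 items 1a-b. Report the day 113 comparison both with all values and with flagged values set to missing. Concomitant medication is already collected at visit 12. An early termination visit soon after a challenge would also need the rescue-kit record, because Protocol 7.8 collects kit medication from the first 24 hours separately.

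Keep the flag to H1 antihistamines. Extending it to all of item 1 would bring in the 8-week systemic steroid entry, although steroids are allowed for a late asthmatic response. A course after day 8 lies 21 days before day 29, and one after day 57 lies 28 days before day 85, so sound readings would be lost. The loss could depend on treatment if the drug affects late responses. Bronchodilators should be left out as well.

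Separately, the sponsor should reconcile the scope of 7.8.1 and SAP 4.4 with the schedule that places the test at day 113. Which way to resolve it is for the sponsor.

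The cost is a sentence or two in the SAP, one data flag and a protocol clarification. Some day 113 values would be missing in one of the two versions. That version relies on missing at random, which is doubtful if antihistamine use follows symptoms that the drug affects, so both versions should be shown.
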